**CLINICAL AND MEDICAL CONTROLLED DOCUMENT (CMCD)
REQUIRED FORM/TEMPLATE**

Identifier	Version	Title	Effective Date
CT24-WI-GL02-RF02	4.0	NON-INTERVENTIONAL STUDY PROTOCOL TEMPLATE FOR SECONDARY DATA COLLECTION STUDY	19-Aug-2022

NON-INTERVENTIONAL (NI) STUDY PROTOCOL

Study information

Title	Clinical outcomes and therapy management among patients with advanced Renal Cell Carcinoma (aRCC) receiving systemic first-line (1L) anti-cancer treatment under daily routine in Germany: Retrospective Chart Review (RENALISTIC study).
Protocol number	A4061099
Protocol version identifier	1.0
Date	19-August-2022
Active substance	
• L01EX Other protein kinase inhibitors
○ L01EX01: sunitinib• L01EK Vascular endothelial growth factor receptor (VEGFR) tyrosine kinase inhibitors
○ L01EK01: axitinib• L01XC: Monoclonal antibodies
○ L01XC31: avelumab
Medicinal product	
• Sunitinib (Sutent®)• Axitinib (Inlyta®)• Avelumab (Bavencio®)
Research question and objectives	
• How is the effectiveness, defined as measurement of beneficial effects under “real world” clinical settings, (e.g. progression-free survival, overall survival and best response) of Tyrosine Kinase Inhibitors (TKI) and/or Immune-Checkpoint-Inhibitors (ICI) as 1L in patients with aRCC?

PFIZER GENERAL BUSINESS

Staff must always refer to and follow the current official electronic document repository version.

This document was created based on

QMS04-GSOP-SD-GL06 9.0 CMCD Forms Template WORD 01-Nov-2021

Page 1 of 36

	
• How are patients with aRCC treated in 1L under daily care conditions in Germany in general and in accordance to medical specialities (urology and medical oncology) and treatment settings (hospitals vs office-based practices)?• Are all patients assigned to individual risk ratings under standard daily care conditions according to a scale developed by the International Metastatic RCC Database Consortium (IMDC) before start of a 1L?• How are patients treated in 1L in different risk rating groups and how is the adherence to national/international guidelines?• What kind of previous and subsequent therapies are administered before and after 1L?• How often are evaluations for PD-L1 expression performed before start of 1L and how many patients are positive (TPS $\geq 1\%$) or negative?• How long are patients treated with TKI + ICI and ICI + ICI in 1L in general and in relation to specific therapies like avelumab + axitinib?• How frequent are dose modifications and early discontinuations and what are the reasons?• Are there differences in the handling of modifications among medical specialities? 
To answer these questions the following objectives are derived:
 
Primary Objective(s):
 
• Progression-free survival (PFS) for 1L therapies, expressed as median and as rates at
--	---

	
timepoints of 6, 9, 12 and 18 months after start of 1L
 
Secondary Objectives:
 
• Overall survival (OS) of 1L therapies, expressed as median and rates at timepoints of 12 and 18 months after start of 1L therapy• Best response in 1L overall and in dependence of administered drug regimen• Progression-free survival of 1L therapies in dependence of specific drug regimen• Pre- and post-treatments (i.e. surgery, radiotherapy, medicinal therapies) before/after TKI + ICI and ICI + ICI in 1L• Duration of response (DoR) in 1L overall and in dependence of administered drug regimen (TKI + ICI or ICI + ICI)• Frequency of dose modifications and temporary/permanent discontinuations of 1L therapies and their reasons• Proportions of modifications by dose reduction compared to skipping single applications Effectiveness (PFS, OS and best response) of administered 1L therapies under real world conditions by medical speciality (urology, medical oncology) and setting (practice, hospital)

2. LIST OF ABBREVIATIONS

Abbreviation	Definition
AE	Adverse Event
AEM	Adverse Event Management
AR	Adverse Reaction
aRCC	Advanced Renal Cell Carcinoma
AWMF	Arbeitsgemeinschaft der Wissenschaftlichen Medizinischen Fachgesellschaften = Working party of scientific medical societies
CR	Complete response
CRF	Case Report Form
CRO	Contract Research Organization
CT	Computer tomography
DCF	Data clarification form
DGHO	Deutsche Gesellschaft für Hämatologie und Onkologie = German Society for Hematology and Oncology
DoR	Duration of response
eCRF	Electronic Case Report Form
EU	European Union
FU	Follow-Up
GCP	Good Clinical Practice
GVP	Good Pharmacovigilance Practices
ICD-10	International Classification of Disease 10.revision
ICI	Immune-Checkpoint-Inhibitors
IEC	Independent Ethics Committee

ICMJE	International Committee of Medical Journal Editors
IFN	Interferon
IMDC	International Metastatic Renal Cell Carcinoma Database Consortium
IRB	Institutional Review Board
IV	Intravenous
MRI	Magnetic resonance imaging
NA	Not applicable
ND	Not done
NIS	Non-Interventional Study
OP	Operation
ORR	Objective response rate
OS	Overall survival
PASS	Post-authorization safety study
PD	Progressive disease
PD-L1	Programmed death ligand-1
PFS	Progression-free survival
PI	Product information
PI	Principle investigator
PR	Partial response
RCC	Renal Cell Carcinoma
RKI	Robert-Koch-Institute
RR	Response rate
SAE	Severe adverse event

SAP	Statistical Analysis Plan
SAR	Severe adverse reaction
SD	Stable disease
TKI	Tyrosine Kinase Inhibitor
TPS	Tumor Propotion Score
TTNT	Time-to-next-therapy
TTP	Time-to-progression
YRR	Your Reporting Responsibility
1L	First-line therapy
2L	Second-line therapy

4. ABSTRACT

Title	Clinical outcomes and therapy management among patients with advanced Renal Cell Carcinoma (aRCC) receiving systemic first-line (1L) anti-cancer treatment under daily routine in Germany: Retrospective Chart Review (RENALISTIC study).
Rationale and background	
In Germany RCC is a rare cancer type with around 15.000 new diagnoses per year and an incidence of 15.7 per 100.000 for men and 7.5 per 100.000 for women (Robert Koch Institute, 2020). Regarding new incidences per year RCC is the 10th most common cancer type in women and 9th most common type in men, whereas the rate of mortality per year due to RCC was lower, 13th position in women with 1,8% and 13th position in men with 2,5% of all cancer-associated deaths (Robert Koch Institute, 2020). Most of the newly diagnosed patients were amendable for radical surgery, but 4.000 – 5.000 patients per year will start a new systemic therapy due to their advanced or metastatic disease. Around 70-80% of the new RCC are diagnosed at an early stage and could be treated by partial or radical surgical resections in a curative intention. At present no neoadjuvant or adjuvant setting is established, but new data with TKIs and/or ICIs could be expected in the next few years. A part of patients with locally aRCC are not suitable for curative treatment by surgery. These patients would be treated like patients with metastatic diseases with systemic therapies under palliative intention. Guidelines of the German Cancer Society (S3-Leitlinie Nierenkarzinom, Arbeitsgemeinschaft der Wissenschaftlichen Medizinischen Fachgesellschaften (AWMF), Nov 2021) and of the German Society for Hematology and Oncology (DGHO 2022) recommend for these patients combinations of ICI + TKI as the preferred 1L therapies for all risk groups. For patients with intermediate and poor risk, a combination of nivolumab plus ipilimumab could be considered as an alternative treatment approach. In patients ineligible for ICI and a low risk rating bevacizumab + INF, pazopanib, sunitinib or tivozanib, with an intermediate risk rating cabozantinib, pazopanib, sunitinib or tivozanib and with a high risk rating cabozantinib or sunitinib are recommended. During the treatment with combinations ICI (pembrolizumab or avelumab) + TKI higher rates of modifications and discontinuations of one or both drugs were seen in the pivotal studies. During the therapy with pembrolizumab + axitinib adverse events (AEs) of any cause led to permanent discontinuation of either drug in 30.5%, discontinuation of


	
both drugs in 10.7%, interruption of either drug in 69.9%, and dose reduction of axitinib in 20.3% of the patients in 1st line RCC of any risk (Rini TI et al, 2019). During the treatment with avelumab + axitinib 42% of the patients had at least one reduction in the dose of axitinib due to AEs and in 8% of the patients AEs led to a discontinuation of both avelumab and axitinib (Motzer R et al, 2019). Based on this, an important objective of this study is to gain more insights how widespread the existing national guidelines are followed for the 1L treatments in this patient population. Additional objectives are to describe the frequencies of dose modifications and temporary/permanent discontinuations as well as the proportions of modifications by dose reductions in connection with drug combination of ICI + TKI and ICI + ICI in the standard care setting of urologists and hematologists in practices and hospitals in Germany.

Research questions and objectives	
 • How is the effectiveness, defined as measurement of beneficial effects under “real world” clinical settings, (e.g. progression-free survival, overall survival and best response) of TKI and/or ICI as 1L in patients with aRCC? • How are patients with aRCC treated in 1L under daily care conditions in Germany in general and in accordance to medical specialities (urology and medical oncology) and treatment settings (hospitals vs office-based practices)? • Are all patients assigned to individual risk ratings under standard daily care conditions according to a scale developed by the IMDC before start of a 1L? • How are patients treated in 1L in different risk rating groups and how is the adherence to national/international guidelines? • What kind of previous and subsequent therapies are administered before and after 1L? • How often are evaluations for PD-L1 expression performed before start of 1L and how many patients are positive (TPS $\geq 1\%$) or negative? • How long are patients treated with TKI + ICI and ICI + ICI in 1L in general and in relation to specific therapies like avelumab + axitinib? • How frequent are dose modifications and early discontinuations and what are the reasons?

- Are there differences in the handling of modifications among medical disciplines?

To answer these questions the following objectives are derived:

Primary Objective(s):

- Progression-free survival (PFS) for 1L therapies, expressed as median and as rates at timepoints of 6, 9, 12 and 18 months after start of 1L

Secondary Objectives:

- Overall survival (OS) of 1L therapies, expressed as median and rates at timepoints of 12 and 18 months after start of 1L therapy
- Best response in 1L overall and in dependence of administered drug regimen
- Progression-free survival of 1L therapies in dependence of specific drug regimen
- Pre- and post-treatments (i.e. surgery, radiotherapy, medicinal therapies) before/after TKI + ICI and ICI + ICI in 1L
- Duration of response (DoR) in 1L overall and in dependence of administered drug regimen (TKI + ICI or ICI + ICI)
- Frequency of dose modifications and temporary/permanent discontinuations of 1L therapies and their reasons
- Proportions of modifications by dose reduction compared to cancelling single applications
- Effectiveness (PFS, OS and best response) of administered 1L therapies under real world conditions by medical specialty (urology, medical oncology) and setting (practice, hospital)

Study Design	This is a retrospective, non-interventional, observational, multicenter, Medical Chart Review project in patients with aRCC, who received a systemic 1L therapy between 01 January 2020 – 31 December 2021 under daily routine conditions in hospitals or practices in Germany. At timepoint of enrollment of patients, all decisions for specific treatment regimen or investigations were already made under discretion of the physicians and in accordance to the routine clinical practice. The study should describe and analyze in part 1 and part 2 for the the treatment situation from adult patients with aRCC in 1L as well as the clinical
---------------------	--

	
outcomes and handling of intolerabilities from combination therapies in 1L under daily routine in general and in relation to specific therapies.
 
Only data from medical records for running therapies between 01 January 2020 - 31 December 2021 will be captured under conditions of full anonymization. Based on the full anonymization a written informed consent by the patients or an advice by participating doctors an Independent Ethical Committee (IEC) regarding accordance with professional law should not be necessary.

Population	
Inclusion criteria for part 1 and 2:
 
 • Patients aged ≥ 18 years old • Patients with histologically/cytologically confirmed renal cell carcinoma (International Classification of Disease 10.revision (ICD)-10 C64) • Full medical information regarding all treatments before, during and after 1L should be available. 
Specific inclusion criteria only for Part 1:
 
 • Patients with locally advanced or metastatic disease and a start of any systemic 1L therapy against RCC between 01 January 2020 and 31 December 2021 
Specific inclusion criteria only for Part 2:
 
 • Patients with locally advanced or metastatic disease, who were treated with a combination of ICI + TKI or ICI + ICI as 1st line therapy against RCC and who had a completion of this therapy between 01 January 2020 - 31 December 2021 with a follow-up period of at least 3 months after completion of the 1L. 
Exclusion criteria for part 1 and 2:
 
 • Patients participating in an interventional clinical study within 30 days before start of 1L.
Outcomes	
The following clinical outcomes are of relevance in the study and should be answered regarding the research questions:
 
Primary Outcome
 
 ○ Progression-free survival in 1L in median and at defined timepoints after start 
Secondary outcomes

	
○ Overall survival rates from start of 1L therapy, expressed as median and at pre-defined timepoints○ Proportions of different therapy protocols used in 1L○ Best responses to 1L therapies○ Duration of response to 1L therapies○ Time-to-progression to 1L therapies○ Time-to-next-therapy to 1L therapies○ Frequency of modifications and discontinuations in 1L○ Reasons for modifications and discontinuations in 1L○ Treatment continuation after modifications and discontinuations in 1L (for all therapies and in relation to specific protocols like axitinib + avelumab or nivolumab + ipilimumab) 
Other Outcomes
 
○ Distribution of 1L therapy by age, gender and risk rating○ Distribution of 1L therapy and frequency of modifications/discontinuations by medical speciality and institution
Variables	For the evaluations of the mentioned clinical outcomes the following parameters will be captured: Part 1: 
○ Demographic data (age, gender, weight, body surface)○ Date of first diagnosis○ Stage and risk rating (IMDC) at first diagnosis and at start of 1L○ Assessments and results of PD-L1 expression○ Non-medicinal pre-treatments (primary operation (OP), cytoreductive nephrectomy, radiotherapy)○ Medicinal pre-treatments (adjuvant, neoadjuvant)○ Location of administration and performing medical discipline○ Administered drugs / protocols in 1L○ If applicable: Reason for ineligibility of ICI○ Dates of administrations for i.v. drugs in 1L○ Duration of 1L treatment○ Dosages per administration○ Dose modifications or drug administration cancelling or interim / permanent discontinuations of single drugs / complete therapy in 1L○ Reasons for modifications, cancelling of single administrations and discontinuations in 1L○ Supportive drugs prescribed during 1L○ Date of first response and best response to 1L incl. date and mode of assessment

- Assessment of first and best response in 1L
- Date of tumor progression
- Reasons for end of 1L
- Subsequent therapies (2L and higher) with drugs/protocol and dates for start / end
- Concomitant diseases and therapeutic medications

Part 2:

If patients will qualify for part 1 and part 2 (completion of 1L and follow-up of at least 3 months after completion), the documented data from part 1 will be transferred to part 2 automatically, so that only additional parameters must be filled in. If patients are newly documented in part 2, all of the parameters have to be documented.

- Demographic data (age, gender, weight, body surface)
- Date of first diagnosis
- Stage and risk rating (IMDC) at first diagnosis and at start of 1L
- Assessments and results of PD-L1 expression as TPS
- Non-medicinal pre-treatments (primary OP, cytoreductive nephrectomy, radiotherapy)
- Medicinal pre-treatments (adjuvant, neoadjuvant)
- Location of administration and performing medical discipline
- Administered drugs / protocols in 1L
- If applicable: Reason for ineligibility of ICI
- Dates of administrations for i.v. drugs in 1L
- Dosages per administration
- Dose modifications or drug administration cancelling or interim /permanent discontinuations of single drugs / complete therapy in 1L
- Reasons for modifications, cancelling of single administrations and discontinuations in 1L
- Supportive drugs prescribed during 1L
- Date of first response and best response in 1L incl. mode of assessment
- Assessment of first and best response in 1L
- Date of tumor progression
- Reasons for end of 1L
- Subsequent therapies (2L and higher) with drugs/protocol and dates for start / end
- Concomitant diseases and therapeutic medications

Data Sources	Source documents (paper or electronic medical charts) are those, in which patient data of daily care are recorded and documented in individual patient files. The data to be collected in the study will be obtained via a specific programmed eCRF. The data in the eCRF should be consistent with the relevant source documents. Medical records should contain demographic data, medical data, treatments and diagnostic documentations according to common practice. The documentation will be performed under full anonymization, so that a re-identification of single patients will not be possible. Based on this anonymization, queries for explanations or changes of data could not be submitted by the data management. All documented variables will be checked by data manager and/or medical lead of GermanOncology in relation to implausibility, inaccuracies or missing data. If implausibility or inaccuracies or missing data of single patients will be of great relevance for analyses, the data management and/or medical lead have the right to reject patients. For such rejected patients no payment will be triggered.
Study Size	Based on public data the population of patients with aRCC and an indication for a 1L therapy is around $n = 4.500 - 5.000$ patients per year (Robert Koch Institute 2020). In the period of 01 January 2020 – 31 December 2021, which is the main period of interest in the study for completing or starting 1L therapies, the total population of patients with aRCC would be around $n = 9.000 - 10.000$ patients. To estimate the needed number of patients in the study to reach adequate representation across Germany, the following common formula is used $n = \frac{z^2 \pi(1 - \pi)N}{z^2 \pi(1 - \pi) + E^2(N - 1)}$ 
N = population of patients with aRCC and indication for 1L = 10.000 patients in 24 months Π = 0,5 (consensus, if attribute is unknown before study) E = margin of error = 5% = 0,05 Z = 1,96 (for confidence interval of 95%)
 
Based on these assumptions (PFS of 1L therapies included in guidelines was 8.4 – 15.1 months in clinical studies) the number of patients needed for representative statement regarding the primary objective (= PFS rates at defined time points under real world conditions) is at least $n = 370$. With a buffer of around 10% the sample size in the study should be $n = 400$ patients with aRCC and 1L therapies in the period from 01 January 2020 – 31 December 2021. Based on published data for PFS it could be

	
assumed for part 2, that also the number of patients with combination therapies in part 2 (n = 300) will grant a representative statement to all research questions. Based on information of urological and oncological experts as well as own data of the GermanOncology ^{*1} network (see below), the following assumptions could be set:
 
• Number of patients with new 1L in urological practices (per practice 1- 3 urologists) = 4 - 6 per year
○ Number of patients with new 1L in period of 24 months = 8 - 12• Number of patients with new 1L in oncological practices (per practice 2- 4 oncologists) = 4 - 6 per year
○ Number of patients with new 1L in period of 24 months = 8 - 12• Number of patients with new 1L in hospitals with urological focus = 8 - 12 per year
○ Number of patients with new 1L in period of 24 months = 16 - 24• Proportion of 1L therapies in urological and oncological practices: 50% : 50%• Proportion of patients treated with 1L in practices and hospitals (as most of therapies are oral therapies): 65% : 35% 
Based on the assumptions the needed number of sites are at least:
 
• Number of urological practices: 15• Number of oncological practices: 15• Number of hospitals with urological focus: 10• Total number of sites across Germany: 40 
<small>^{*1} GermanOncology operates a permanent network of 25 oncological practices across Germany, is collecting longitudinal RWE data about several tumor entities since 2012 and is able to analyze data from more than 25.000 patients with around 25 different tumor entities</small>

Data Analysis	
The following clinical outcomes will be measured:
 
Primary outcome:
 
○ PFS in 1L:
▪ described as median and rates of patients without disease progression or death for any cause at defined timepoints (6, 9, 12 and 18 months) after start of 1L therapy. 
Secondary outcomes:
 
○ OS in 1L

	
 ▪ Defined as median and rates of patients alive at pre-defined timepoints (12 and 18 months) after start of 1L therapy. ○ Proportion of different drug regimen in 1L 
 ▪ Defined as percentages of therapy protocols used as 1L therapy. ○ Best response rate (RR) in 1L 
 ▪ Defined as best response (complete response (CR) / partial response (PR) / stable disease (SD) / progressive disease (PD) / not done (ND)) recorded from the start of the therapy until disease progression/recurrence based on investigator's assessment. A confirmation of response is not required. ○ Duration of Response (DoR) in 1L 
 ▪ Defined as time from documentation of first disease response to disease progression. ○ Time to progression (TTP) in 1L 
 ▪ Defined as time from start of therapy until objective disease progression without including deaths. ○ Time to next treatment (TTNT) in 1L 
 ▪ Defined as time from last drug administered to initiation of next therapy. ○ Dose modifications and discontinuations in 1L 
 ▪ Defined of number of patients with at least 1 dose modification (reduction of dose or cancelling of administration) or with an interim/permanent discontinuation of one or all drugs of a therapy. ○ Handling after dose modification or discontinuations in 1L 
 ▪ Defined as continuation of therapies after dose modifications or temporary/permanent discontinuation of single drugs. 
The clinical outcomes will be analyzed for the total group of all patients and for following subgroups:
 
 ○ Age: < 70 years vs. ≥70 years ○ Gender: male vs. female ○ Risk rating: favorable (low) vs. intermediate vs poor (high) risk ○ Medical disciplines: urology vs. medical oncology ○ Institutions: practices vs. hospitals
Milestones	
Planned milestones:
 
 ● Start of data collection: 1 October 2022 ● Interim analysis (expected): 31 October 2022 ● End of data collection: 30 January 2023 ● Final study report: 15 April 2023

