9.3. Data sources

Source documents (paper or electronic medical charts) are those, in which patient data of daily care are recorded and documented in individual patient files. The data to be collected in the study will be obtained via a specific programmed eCRF. The data in the eCRF should be consistent with the relevant source documents. Medical records should contain demographic data, medical data, treatments and diagnostic documentations according to common practice. The documentation will be performed under full anonymization, so that a re-identification of single patients will not be possible. Based on this anonymization, queries for explanations or changes of data could not be submitted by the data

management. All documented variables will be checked by data manager and/or medical lead of GermanOncology in relation to implausibility, inaccuracies or missing data. If implausibility or inaccuracies or missing data of single patients will be of great relevance for analyses, the data management and/or medical lead have the right to reject patients. For such rejected patients no payment will be triggered.

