9.7. Quality control

The most relevant step in quality control and quality assurance will be an avoidance of inaccuracies or mismatches in terminology by data entries in data fields over a selection of parameters or descriptions out of pre-defined drop-down-lists. Free text is only intended for descriptions after selection of "other", which will be possible in some data fields, where a pre-definition cannot be

implemented for 100%. For all dates regarding parameters like first diagnosis, pre-treatments, therapy administrations automatic checks are implemented for data entries, so that the course of treatment will be shown correctly (e.g. adjuvant therapy after OP and before palliative therapy, end of 1L before start of 2L, end of therapy after last administration). In defined data fields new explanation fields will open up after selection of specific documentations (e.g. after selection of dose modification query for modified dose, after selection of end of therapy query for reason). In data fields with information like weight, height or age, automatic standard range checks, are implemented to avoid input errors. In addition to these automatic checks every data entry will also be checked by an experienced data manager and, if needed, by the medical lead.

In case of relevant inaccuracy or implausibility, patient's data files will be rejected before further analytical processes will start. After the decision for rejection of patients the investigator will be informed about the reason for rejection and all data will be deleted immediately.

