10.1. Patient information

All parties will comply with all applicable laws, including laws regarding the implementation of organizational and technical measures to ensure protection of documented patient data. Such measures will include omitting patient names or other directly identifiable data in any reports, publications, or other disclosures, except where required by applicable laws.

The documented patient data will be stored at the study site in encrypted electronic form and will be password protected to ensure that only authorized study staff have access. The study site will implement appropriate technical and organizational measures to ensure that the documented patient

data can be recovered in the event of disaster. In the event of a potential documented patient data breach, the study site shall be responsible for determining whether a documented patient data breach has in fact occurred and, if so, providing breach notifications as required by law.

To protect the rights and freedoms of natural persons with regard to the processing of documented patient data, when study data are compiled for transfer to Pfizer and other authorized parties, patient names will be removed and will be replaced by a single, specific, numerical code, based on a numbering system defined by Pfizer. All other identifiable data transferred to Pfizer or other authorized parties will be identified by this single, patient-specific code. In case of data transfer, Pfizer will maintain high standards of confidentiality and protection of patients' documented data consistent with the clinical study agreement and applicable privacy laws.

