10.3. Institutional review board (IRB)/Independent ethics committee (IEC)

There must be prospective official statement or approval of the study protocol, protocol amendments, and other relevant documents (e.g., informed consent forms if applicable) from the relevant IRBs/IECs. All correspondence with the IRB/IEC must be retained. Copies of IRB/IEC approvals must be forwarded to Pfizer.

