All the demographic fields on the NIS AEM Report Form may not necessarily be completed, as the form designates, since not all elements will be available due to privacy concerns with the use of secondary data sources. While not all demographic fields will be completed, at the very least, at least one patient identifier (e.g., gender, age as captured in the narrative field of the form) will be reported on the NIS AEM Report Form, thus allowing the report to be considered a valid one in accordance with pharmacovigilance legislation. All identifiers will be limited to generalities, such as the statement “A 35-year-old female...” or “An elderly male...” Other identifiers will have been removed.

Additionally, the onset/start dates and stop dates for “Illness,” “Study Drug,” and “Drug Name” may be documented in month/year (mmm/yyyy) format rather than identifying the actual date of occurrence within the month /year of occurrence in the day/month/year (DD/MMM/YYYY) format.”>

All research staff members must complete the following Pfizer training requirements:

- *“Your Reporting Responsibilities (YRR) Training for Vendors.”*

These trainings must be completed by research staff members prior to the start of data collection. All trainings include a “Confirmation of Training Certificate” (for signature by the trainee) as a record of completion of the training, which must be kept in a retrievable format. Copies of all signed training certificates must be provided to Pfizer.

|Re-training must be completed on an annual basis using the most current Your Reporting Responsibilities training materials.

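### The protocol gives two instructions on ethics review and two accounts of data status, and its no-query rule deletes eligible patients' files without correction or any record of the loss

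*Combined protocol and SAP*

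**What the plan says.** **Ethics review.** The Abstract, under Study Design, rests on full anonymization the view that neither written consent nor advice from an "Independent Ethical Committee (IEC) regarding accordance with professional law should not be necessary". Section 10.3 states: "There must be prospective official statement or approval of the study protocol, protocol amendments, and other relevant documents". It asks for this from the relevant committees and wants copies of approvals sent to the sponsor.

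**Data status.** Section 9.3 says that individual patients cannot be re-identified. Section 9.5 says that each file carries a random alphanumeric code generated by the system, and that the sponsor gets only anonymous or aggregated data that cannot be traced to a patient or site. Section 10.2 says that the study involves no data under privacy law. Section 10.1 says that, when data are compiled for transfer, "patient names will be removed and will be replaced by a single, specific, numerical code, based on a numbering system defined by Pfizer". It adds that other identifiable data go to the sponsor under that code, and that privacy law and breach notification apply.

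**Queries and rejection.** Section 9.3 says that, because of anonymization, "queries for explanations or changes of data could not be submitted" by data management. Files with material problems may be rejected. Section 9.7 says that after a rejection "the investigator will be informed about the reason for rejection and all data will be deleted immediately".

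**The concern.** A site that follows the Abstract could begin abstraction without any ethics statement, while a site that follows section 10.3 would wait for one. The timetable is short. The protocol is dated 19 August 2022, collection runs from 1 October 2022 to 30 January 2023, and Table 1 contains no ethics milestone.

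The same premise, full anonymity, carries both the ethics and consent waiver and the ban on queries. If the data are in fact coded, neither follows as written.

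The statistical stake is in the second use. Section 9.1.2 asks sites to document all their eligible patients, and section 9.6 analyses all evaluable ones. Between those two points files can be rejected by judgement and erased. If rejection is related to how well a chart was kept, and that is related to site type, regimen or outcome, then the distribution of therapies, progression-free survival and the frequency of dose modifications describe a selected group. Nothing would remain with which to examine the selection.

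**Working it through.** No arithmetic bears on the core of this point; it is a comparison of texts.

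1. **Are both sides current?** Section 5 lists no amendments, so no passage is superseded by another.

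2. **Ethics.** The Abstract says that advice should not be needed, on the ground of anonymity. Section 10.3 says that a prospective statement or approval must exist and has no carve-out for anonymous data. Nothing in the protocol ranks one above the other or says that they concern different steps.

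3. **Data status, item by item.**
   - *Code:* random and machine-generated (9.5), against a numerical code on a sponsor-defined system (10.1).
   - *What reaches the sponsor:* anonymous or aggregated data only (9.5), against identifiable data under a patient-specific code (10.1).
   - *Privacy law:* not engaged (10.2), against engaged (10.1).

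   These are different descriptions of one data flow. Section 10.1 reads as coded data; sections 9.3, 9.5 and 10.2 read as anonymous data.

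4. **Does the no-query rule follow from anonymity?** Section 9.5 provides a correction history that records who corrected and when. Section 9.5.1 requires signed forms that match the charts. Section 9.5.2 has sites keep copies of all case report forms. Section 9.7 sends the investigator the reason why a particular file was rejected. So a message about a single file can reach the site that entered it. Barring a query while sending a rejection notice is not explained by anonymity.

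5. **What follows for the analysis set.** The grounds for rejection are qualitative: problems judged to matter greatly for the analysis (9.3), or a large amount of missing data (9.8). No threshold is set. Section 9.5 requires a reason for each rejection, but no section provides for a log of rejected files, and section 9.7 removes the data at once. It is also not said whether the copies under 9.5.2 include rejected files. As planned, the study could not report rejected patients by type or compare them with those retained.

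**The case against.** The best defence starts with the Abstract's wording, which is hedged and garbled. It speaks of professional law and participating doctors, so it may waive only each doctor's own advice while a study-level statement is still obtained. That reading is possible, but the protocol does not state it.

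The defence also points to existing controls: drop-down lists, automatic date and range checks, mandatory fields, and a rejection power that is discretionary and limited to material problems. This stands in part. These controls will stop many errors at entry, but they do nothing for a file that is later found faulty.

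Four stronger readings are tempting, and the documents do not support them.

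- **That rejections would take the study below its minimum size.** The plan's formula gives 0.9604 × 10,000 / (0.9604 + 0.0025 × 9,999) = 9,604 / 25.958 = 370, and the target is 400. Falling below 370 needs an assumed rejection rate and no replacement. Enrolment is competitive without a site cap (9.1.2), sites may be added (9.1), and the plan's own site figures give 30 × 8–12 + 10 × 16–24 = 400–600 patients. Even if 10% of 400 were lost (an assumption) and not replaced, 360 would give a margin of 1.96 × √[(0.25/360) × (9,640/9,999)] = 5.07%, against 5.00% at 370. Precision is not the issue. Replacement restores numbers but does not undo selection.
- **That section 11 contradicts Table 2 on dates.** Table 2 collects full calendar dates, and section 11 says that certain dates "may be documented in month/year (mmm/yyyy) format rather than identifying the actual date of occurrence". Section 11 governs the safety report form, and only permissively. It sets no rule for the eCRF.
- **That the rejection notice proves that patients are re-identifiable.** It shows traceability to the site. No section says that a site holds a key linking file code to chart.
- **That intervals could replace calendar dates at no loss.** The eligibility windows in section 9.1.1 are calendar windows and could then no longer be verified in the exported data.

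**Conclusion.** The point holds as an internal inconsistency with one consequence for the analysis. The Abstract and section 10.3 give conflicting instructions on ethics review. Section 10.1 conflicts with sections 9.3, 9.5 and 10.2 on the code, on what is transferred and on the application of privacy law. The no-query rule is not justified by the reason given for it. Combined with immediate deletion, it leaves the evaluable set open to selection on record quality that cannot be checked.

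The size of that selection, and its direction, cannot be derived: the documents give no expected rejection rate and no link between record quality and outcome. A reader might infer that the study breaches a legal duty to obtain an ethics statement. Whether the law requires one cannot be decided from the documents, and the conclusion does not depend on it. It rests only on the current wording of the sections named. The matter should be settled before collection starts; it is cheap to settle.

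**What to change.** 1. Reconcile the Abstract with section 10.3 so that a single instruction applies to all sites, and enter the resulting ethics step in Table 1 ahead of the first chart abstraction.
2. Use one description of the data status and one description of the code in sections 9.3, 9.5, 10.1 and 10.2. Align the consent, ethics and query rules with it, and state whether a site can trace a file code to a chart.
3. Before deleting a file, return the section 9.7 reason to the entering site, by eCRF file code, as a correction request with a short deadline. Delete only if it stays unresolved. Keep a log of the number of rejected files and the reasons, by site type and regimen, and report it with the results.

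The cost is protocol wording, one extra step on a route that already carries rejection notices, and a simple log. Data management takes on some additional work, and the start may be delayed at some sites. If no site can trace a file to its chart, the correction step will resolve fewer files, but the log still shows what was lost.
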